### 3.2 Secondary endpoints:

- Overall response rate at Day 56 on the lower GI tract MAGIC stage: defined as proportion of subjects with complete response (CR) or partial response (PR) on the lower GI tract MAGIC stage at Day 56.
- Overall response rate (PR and CR) at Days 14, 28, 91, 119, 147, and 182 on the lower GI tract MAGIC stage.
- Overall response rate (PR and CR) at Days 14, 28, 56, 91, 119, 147, and 182 by organ system (skin, lower and upper GI tract, and liver) on the total MAGIC grade.
- Proportion of all subjects who achieve a CR or PR at Day 28 and maintain a CR or PR at Day 56 [Only for Primary Analysis].
- Individual duration of lower GI response (according to the MAGIC score)
  - counted from the first response to return to baseline or worse
  - in subjects that were re-treated with apaglutide because of a lower GI-aGVHD flare, counted from the first response after apaglutide restart to return to baseline or worse
- Time to:
  - Partial lower GI-aGVHD response as defined by the MAGIC score
  - Complete lower GI-aGVHD response as defined by the MAGIC score
- Duration of response from Day 56 on the total MAGIC score: defined as the interval from the Day 56 response (PR and CR) to death or new systemic therapy for aGVHD (including an increase in steroids >2 mg/kg/day methylprednisolone (MP) equivalent), whichever occurs first, with at least 182 days of follow-up
- Duration of response from Day 28 on the total MAGIC: defined as the interval from the Day 28 response (PR and CR) to death or new systemic therapy for aGVHD (including an increase in steroids >2 mg/kg/day MP equivalent), whichever occurs first, with at least 182 days of follow-up
- Best overall response defined as overall response (PR or CR) at any time point up to and including Day 91 and before the start of additional systemic therapy for lower GI-aGVHD [Only for Primary Analysis]
- Failure-free survival up to 2 years post-first dose of apaglutide
- Incidence of malignancy relapse up to 2 years post-first dose of apaglutide [Only for EOT Analysis]
- Non-relapse mortality up to 2 years post-first dose of apaglutide

- Overall survival up to 2 years post-first dose of apaglutide [Only for EOT Analysis]
- Incidence of lower GI-aGVHD flare up to Day 182 after the first apaglutide dose following earlier cessation due to complete lower GI-aGVHD response
- Incidence of graft failure up to 2 years post-first dose of apaglutide [Only for EOT Analysis]

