#### 4.1.1 *Definition of Baseline, Analysis Visits, Visit Window*

Baseline is defined as the last measurement prior to the first administration of the trial treatment (i.e. first administration of apraglutide). The last available scheduled or unscheduled assessment collected on or before the date of start of trial treatment will be flagged as the baseline assessment. If both time of assessment and time of treatment start are captured (such as labs), the last available assessment before the treatment start date/time will be used for baseline.

For questionnaires, baseline is defined as the form completed at the baseline Visit.

Scheduled visits will be assigned to analysis visits as recorded on the electronic case report form (eCRF).

Visit windowing will not be used for handling unscheduled visits. Instead, all unscheduled visits will be assigned a visit name of “Unscheduled”. Such visits will be included in data listings and will contribute to the derivation of best- or worst-case values where applicable.

Analysis day will be calculated in reference to the date of the first administration of apraglutide. The day of the first administration of the investigational medicinal product (IMP) will be “analysis day 1”, and the day immediately before analysis day 1 will be “analysis day -1”. There will be no analysis day 0.

Each date will be assigned an analysis day calculated as follows:

- if the date < first dose date then analysis day = (Assessment date/Event date – first dose date)
- if the date  $\geq$  first dose date then analysis day = (Assessment date/Event date – first dose date) +1.

The analysis day will be used to compute duration for time-to-event endpoints.

The visit labels will correspond to the ones reported in the Schedule of Assessments. For instance, Visit Day 7 corresponds to a visit occurring at analysis day  $8 \pm 1$  day (i.e., between analysis day 7 and analysis day 9).

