#### 4.3.9.2 Overall/Lower GI Response Based on MAGIC Score by Time Point

The Lower GI MAGIC score response and the total MAGIC score response will be calculated per the definition described in Appendix A based on the Lower GI MAGIC score and the total MAGIC score, respectively, at a given time point, compared to the corresponding score at Baseline. It follows that every observed Lower GI MAGIC Stage response at a time point will be classified as *Progression, Stable Disease, Partial Response, and Complete Response*. Similarly, every observed Total MAGIC score response will be classified into the same categories augmented by the Mixed Response category. Subjects with missing MAGIC assessments after the first dose of apraglutide will be included as non-responders for response rate calculation. Censored assessments will not be included in the response rate calculation. Note: if a subject initiated an additional, new systemic therapy for an earlier progression, mixed response, or non-response of aGVHD, both the lower GI-aGVHD response and the overall response at subsequent time points will be assigned as non-responders until the clinical cut-off date. Additional new systemic therapies are only those that started after the first dose of apraglutide and are captured in the CM and PR eCRF forms.

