*4.3.9.6 Durable overall response on the Total MAGIC Score from Day 56 to Day 91*

Durable overall response rate from Day 56 to Day 91 on the Total MAGIC Score is defined as proportion of subjects who had a response (either CR responder or PR responder) on the total MAGIC score at Day 56 and remain a CR responder or PR responder on the total MAGIC score at Day 91.

Percentage is computed using the number of subjects in treatment group as denominator.

The analysis of the durable overall response rate from Day 56 to Day 91 on the Total MAGIC Score will be performed similarly to the analysis of durable overall response on the Lower GI MAGIC score described in Section 4.3.9.5.

*4.3.9.7 Individual duration of lower GI response*

Duration of lower GI response is defined as the duration from the first date a subject is identified as a Lower GI MAGIC Score CR or PR responder until the next date a subject is Lower GI MAGIC Score SD/PD (i.e., return to baseline or worsening), or dead, whichever occurs first.

This is only defined for subjects with partial response or complete response. The best response is derived from assessments performed from the start of the treatment up to Day 91 or the start of additional systemic therapy for GI-aGVHD, whichever occurs first.

Subject for which neither “return to baseline or worsening” or “dead” event occurs will be right censored at their last MAGIC assessment visit. The ICE events and strategies defined in section 4.3.9.2. will be applied consistently for the estimation of CR and PR.

The event or censoring date will be determined based on the conventions listed in Table 4-3.

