**Table 4-3: Date of Event or Censoring for Duration of Lower GI Response**

Situation	Date of event or censoring	Outcome	Event Description or Censoring Reason
Lower GI MAGIC score SD/PD before additional systemic therapy for aGVHD	First MAGIC assessment showing SD or PD, whichever occurs first	Event	SD/PD
Death without Lower GI MAGIC score SD/PD and not receiving additional systemic therapy for aGVHD	Date of death	Event	Death
Missing lower GI MAGIC assessment	Date of last evaluable MAGIC assessment before the first missed visit	Event	Missing visit
Additional systemic therapy for aGVHD used for any earlier progression, mixed response or stable aGVHD.	Date of last evaluable MAGIC assessment before additional systemic therapy for aGVHD	Event	Treatment Failure
Alive and without: Lower GI MAGIC score SD/PD, or missing, or initiation of additional systemic therapy for aGVHD	Date of last evaluable MAGIC assessment	Censored	Clinical cut-off date

Duration of Lower GI response will be summarized using Kaplan-Meier estimator. The number and percentage of subjects experiencing an event, and subjects censored will be summarized by apraglutide dose levels and in total. The median time-to-event will be presented where possible, along with the range and the associated two-sided 95% Brookmeyer-Crowley confidence interval. The event-free rate with 95% CI using Greenwood's formula will be provided for selected time points (e.g., 1, 3, 6, 12 and 24 months). Plots of the Kaplan-Meier estimate for the duration of Lower GI response will be presented by apraglutide dose levels and in total.

4.3.9.8 *Time to partial and complete lower GI-aGVHD response as defined by the MAGIC score*

Time to partial lower GI-aGVHD response is defined as the time from the first injection of apraglutide to the first partial response lower GI assessment according to MAGIC score. This is only defined for subjects with partial response. The ICE events and strategies defined in section 4.3.9.2 will be applied consistently for the estimation of CR and PR.

Time to complete lower GI-aGVHD response is defined as the time from the first injection of apaglutide to first complete response lower GI assessment according to the MAGIC score. This is only defined for subjects with complete response.

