
“Additional systemic therapy” definition for the complete and partial response definition
	
Any GVHD systemic therapy being started after apaglutide initiation to achieve GVHD control, i.e. any medication or procedure marked as Reason for medication = “aGVHD treatment” and “Is this an additional, new systemic therapy for an earlier progression, mixed response or non-response of aGVHD?” = Yes in the CM or PR page of the eCRF.
 
Note:
 
 
- Increases or addition of a new systemic steroid will not be counted as new or additional GVHD therapy.
 
Budesonide and beclametasone not to be considered as new GVHD therapy
 
- Change in dose of CNIs will not be considered as additional GVHD therapy if already given prior to apaglutide
 
 
New CNIs after apaglutide initiation should be considered as a new systemic therapy, if marked as “aGVHD treatment” and “Is this an additional, new systemic therapy for an earlier progression, mixed response or non-response of aGVHD?”; these will not be considered as new therapy if marked as “prophylaxis for a drug side effect”.

Complete lower gastrointestinal (GI)-aGVHD response
	
The resolution of all lower GI-aGVHD signs and symptoms (score of 0 for aGVHD grading) of GVHD without administration of additional systemic therapies for any earlier progression, or non-response of lower GI-aGVHD.

Partial response
	
An improvement of one stage in one or more organs involved with aGVHD signs or symptoms without progression in other organs or sites without administration of additional systemic therapies for an earlier progression, mixed response, or non-response of aGVHD

Partial lower GI-aGVHD response
	
An improvement of one stage in the signs and symptoms of lower GI-aGVHD without administration of additional systemic therapies for any earlier progression or non-response of lower GI-aGVHD.

Lack of response	Defined as stable disease, mixed response, or progression
Stable disease	An absence of improvement in all organs involved by aGVHD, without worsening in all involved organs or development of signs or symptoms of aGVHD in a new organ
Stable disease (lower GI-aGVHD)	An absence of improvement or absence of worsening in lower GI-aGVHD
Mixed response	An improvement of at least 1 stage in the severity of aGVHD in one organ accompanied by progression in another organ or development of signs or symptoms of aGVHD in a new organ

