Progression	Worsening in one or more organs by one or more stages without improvement in any other involved organ
Lower GI-aGVHD progression	Worsening in lower GI-aGVHD per MAGIC lower GI-score compared with baseline
Lower GI-aGVHD flare	
Any increase in signs or symptoms of lower GI-aGVHD that is sustained for >24 hours after an initial response (CR or PR) and requires re-escalation of immunosuppressive therapy (e.g., corticosteroid, calcineurin inhibitors and/or ruxolitinib dosing).
 
While all aGVHD flares will be captured during the trial whether occurring during steroid, CNI, BAT or ruxolitinib taper, only flares that fulfil either one the following criteria will be considered a failure of treatment:
 
 
1. Addition of new systemic therapy for lower GI-aGVHD due to inability to taper corticosteroids below methylprednisolone (MP) 0.5 mg/kg/day (or equivalent <0.6 mg/kg/day of prednisone) for a minimum 7 days
 
 
OR
 
 
2. Addition of new systemic therapy for lower GI-aGVHD due to re-escalation of corticosteroids to MP >2 mg/kg/day (or equivalent >2.5 mg/kg/day of prednisone)
 

Best overall response	The best response recorded from the start of the treatment up to Day 91 or the start of additional systemic therapy for GI-aGVHD

Best overall lower GI-aGVHD response	The best response of Lower GI-aGVHD response recorded from the start of the treatment up to Day 91 or the start of additional systemic therapy for GI-aGVHD
--------------------------------------	---

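### Response to flare re-treatment is scored against the stage before the first-ever dose, so a subject who flares below that stage counts as a responder at restart without improving

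*SAP*

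**What the plan says.** SAP 4.1.1 sets one baseline for everything except questionnaires: "Baseline is defined as the last measurement prior to the first administration of the trial treatment". No second baseline is defined at flare or at restart. SAP 4.3.9.2 derives lower GI response from the score "at a given time point, compared to the corresponding score at Baseline".

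SAP 3.2 lists two durations of lower GI response. One covers the first response. The other covers re-treated subjects and runs from the first response after "restart to return to baseline or worse". Protocol 1.5.2.2 words both in the same way. SAP 4.3.9.7 derives only one duration, from the first CR or PR "until the next date a subject is Lower GI MAGIC Score SD/PD (i.e., return to baseline or worsening), or dead, whichever occurs first". It gives the re-treatment endpoint no start rule, reference stage or censoring rule of its own. Table 4-3 adds two further events: a missed MAGIC assessment, and "Additional systemic therapy for aGVHD used for any earlier progression, mixed response or stable aGVHD". It has no row for a flare or for an apraglutide restart.

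SAP Appendix A defines a flare as "Any increase in signs or symptoms of lower GI-aGVHD that is sustained for" more than 24 hours after an initial response, where the increase also "requires re-escalation of immunosuppressive therapy". On what counts as additional systemic therapy, Appendix A states: "Increases or addition of a new systemic steroid will not be counted as new or additional GVHD therapy". It likewise leaves out dose changes of a calcineurin inhibitor (CNI) already given before apraglutide. A new CNI entered as aGVHD treatment for an earlier failure does count.

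**The concern.** Re-treatment has its own secondary objective (Protocol 1.5.1.2), and the question there is whether a second course helps a subject who has flared. That needs a reference taken at the flare. A flare is any sustained worsening that needs more immunosuppression, so it can stop short of the stage at trial entry. Such a subject is still better than at entry, and the general rule calls that a partial response. The response after restart then begins at the first assessment, whatever the second course does, and continues for as long as the stage stays below the entry value.

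The same rule affects the first response. A below-baseline flare is neither stable disease nor progression against the entry stage. Unless a counted therapy is started or an assessment is missed, the first response therefore continues through the flare and the second course, and its duration does not show that control was lost.

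**Working it through.** The plan gives no figure to reproduce, so the check applies its rules to every case.

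**Inputs.** Baseline lower GI stage is 1 to 4 (Protocol 2.2 and inclusion criteria). Flare stage is taken as 1 to 4. Classification against the original baseline follows SAP 4.3.9.2 and Appendix A: Stage 0 is CR, below baseline is PR, equal is SD, above is PD. Appendix A describes PR as an improvement of one stage. It is read here as at least one stage, because 4.3.9.2 puts every observed result into one of these four classes and a two-stage improvement short of Stage 0 fits no other.

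**Class at restart if the stage has not changed since the flare:**

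| Baseline | Flare 1 | Flare 2 | Flare 3 | Flare 4 |
|---|---|---|---|---|
| 1 | SD | PD | PD | PD |
| 2 | PR | SD | PD | PD |
| 3 | PR | PR | SD | PD |
| 4 | PR | PR | PR | SD |

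PR cells: 0 + 1 + 2 + 3 = 6 of 16. In these the subject is a responder at the first assessment after restart without improving from the flare. The other 10 cells (4 SD, 6 PD) end the first response and give no automatic credit. If the flare stage is the reference instead, an unchanged stage is SD in every cell, and the 6 fall to 0.

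The grid omits flares that worsen symptoms but stay at Stage 0. Against the original baseline these score CR. Against a Stage 0 reference no improvement is possible.

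**Does the re-escalation that defines a flare stop the clock?** Appendix A gives corticosteroid, CNI and ruxolitinib dosing as examples. Steroid increases and dose changes of an existing CNI are expressly not additional therapy. Re-escalating ruxolitinib is not starting a new therapy. Neither flare nor restart is among ICE1 to ICE10 in 4.3.9.2. Protocol 4.2.3.3 prohibits other systemic GVHD therapy during the trial, so a flare managed within the protocol will often trigger no event.

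**Illustration.** Assume baseline Stage 3, CR first reached at Day 56, apraglutide stopped, flare to Stage 1 at Day 119 with restart, first assessment after restart at Day 126, and Stage 1 held to Day 182 with no missed assessment and no counted therapy.

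- First-response duration as written: 182 − 56 = 126 days, and still running.
- First-response duration if the flare ended it: 119 − 56 = 63 days.
- Re-treatment response credited with no improvement from the flare: 182 − 126 = 56 days, overlapping the first.

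**The case against.** The strongest reply is that the SAP gives no derivation for the re-treatment endpoint, so scoring against the original baseline is an inference and the fault is only missing detail. It is true that no sentence names the reference for re-treated subjects. But 4.1.1 and 4.3.9.2 are general rules with no exception for re-treatment, and a programmer following them would produce this result. If another reference was intended, it is not written down.

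Second, the wording comes from the protocol. That stands, and it means the correction is a departure from a protocol-specified secondary endpoint that has to be recorded as one.

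Third, for the first response, time until all improvement since entry is lost is a coherent quantity. Flares are summarised separately (4.3.9.15), and duration from Day 28 or Day 56 on the total score already stops at new systemic therapy or steroids above 2 mg/kg/day (4.3.9.9). This also stands. Whether a below-baseline flare should end the first response is partly a choice of estimand, which argues for a supportive analysis and against replacing the definition.

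Fourth, the practical effect may be small. At most 34 subjects are planned, re-treatment needs an earlier stop for response followed by a flare between Weeks 9 and 25, and 4.3.9.15 reduces flare data to a listing if 5 or fewer subjects flare. A listing that shows stages would reveal an unchanged stage. The point limits the size but does not remove it, because the first-response Kaplan-Meier estimate is produced regardless.

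A reader might also infer that no flare ends the first response. The documents do not support that: a flare at or above baseline, a missed assessment, or a counted new therapy (including a new CNI entered as aGVHD treatment) each ends it.

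**Conclusion.** The point holds for re-treated subjects with baseline Stage 2 to 4 whose flare is Stage 1 or more but below baseline. As written, the re-treatment duration endpoint can credit a second course that changed nothing. Where the flare is managed without a counted additional therapy and no assessment is missed, the first-response duration also runs through it.

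The size is 6 of 16 stage combinations. The combinations are not equally likely, and the documents give no stage or flare frequencies, so no expected number of subjects follows. The 126 against 63 days belongs to one constructed subject and is not an average. The result rests on the general baseline rule applying to re-treatment and on PR meaning at least one stage of improvement.

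Two stronger conclusions may tempt a reader. One is that the re-treatment objective cannot be answered at all. That goes too far, since flares at or above baseline are not credited automatically and a listing with stages would still inform. The other is that the overlapping days are double counted. The two durations are separate summaries and are never added, so the overlap shows the definitions conflict in meaning but does not inflate a total.

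**What to change.** In SAP 4.3.9.7, give the re-treatment endpoint its own derivation:

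- The reference is the last lower GI MAGIC stage before the first re-treatment dose.
- Response is an improvement of at least one stage from that reference. It ends when the stage is back at the reference or higher, or at death. The other Table 4-3 rules are unchanged.
- Subjects whose reference stage is 0 are listed as not evaluable for re-treatment response.
- The original-baseline version stays as supportive. It also shows the reverse case, such as baseline Stage 2, flare Stage 4, improved to Stage 3, where the subject responds to re-treatment but is worse than at entry.
- SAP Section 6 records the change from the protocol wording.

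For the first response, keep the protocol definition and add a supportive Kaplan-Meier analysis in which the first lower GI flare is an event dated at the flare, whether or not it was re-treated. Tying the event to apraglutide restart would give identical flares different durations, because restart is optional.

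No new data are needed. MAGIC is scheduled at the flare-treatment dosing visits (SAP Table B1), and Protocol 5.5 has the date of recurrence and organ staging entered in the eCRF. The cost is a little extra programming, and some reported durations may be shorter.

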### 3.3 Exploratory endpoints

- Pharmacokinetics of apaglutide assessed with a population PK (pharmacokinetic) approach. Absorption rate constant (ka), apparent clearance (CL/F), and apparent volume of distribution (Vz/F) with their intra- and inter-individual variability derived using a nonlinear mixed effects modeling approach, from sparse samples.
- Quality of life and changes in subject-reported outcomes from baseline (EuroQol 5 dimensions-5 levels [EQ-5D-5L], Functional Assessment of Cancer Therapy – Bone Marrow Transplantation [FACT BMT]).
- Global assessment questionnaires (Physician Global Assessment of Disease, Patient Global Assessment of Severity, and Patient Global Assessment of Change).
- Body weight and parenteral support (volume and caloric content) at Days 14, 28, 56, 91, 119, 147, and 182 compared with baseline.
- Individual need for blood transfusions (cumulative bags per subject) assessed from baseline to Day 91 [Only for Primary Analysis].
- Biomarker expression, clinical chemistry parameters, and lower GI histology (when available) related to GI-aGVHD, GI regeneration, and GI barrier function as assessed at baseline and at times indicated in the schedule of assessments:
  - Citrulline (measure of intestinal repair and regeneration) in serum
  - Regenerating islet-derived protein 3 alpha (REG3 $\alpha$ ) in serum
  - Suppression of tumorigenicity 2 (ST2) in serum
  - MAGIC algorithm probability (MAP) score consisting of REG3 $\alpha$  and ST2
  - Angiopoietin-1 and -2 in serum
  - Soluble thrombomodulin (sTM) in serum
  - Vascular endothelial growth factor (VEGF) in serum

- Albumin in serum
- Bilirubin in serum
- Presence of intestinal cell lines (L-cells, Paneth cells, intestinal stem cells) and status of mucosal architecture (crypts, villi) from histology slides of lower GI biopsies before apraglutide treatment and at the Day 56 visit (when biopsy data are available)
- Calprotectin in stool
- Microbial constitution of the stool microbiome
- Time to discharge from hospital, number of readmissions to an inpatient setting and duration of readmissions up to Week 26

